6.4.2 Sample Size Considerations

An a priori power analysis conducted through G*Power (Universität Kiel, v. 3.1.9.2) estimated a conservative sample size analysis for the RCT. We are expecting a total of 140 participants, given the length of the trial, we estimate 20% attrition rate of the final sample, giving us a total sample of (n=36) per group, for a final sample size of 108. The power analysis is based on previously utilized research in which estimated effect sizes ranged from 20 to 40 individuals per group (52). We will attempt to enroll equal numbers of male and female individuals to evaluate gender differences through urn randomization process.

52. Hancock, G. R. and R. O. Mueller, Eds. (2010). *The Reviewer's Guide to Quantitative Methods. Power Analysis*. New York, NY, Routledge.

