5. Chronic pain acceptance Chronic Pain Acceptance Questionnaire-Revised (CPAQ-Revised) 20-item scale designed to measure acceptance of pain. The acceptance of chronic pain is thought to reduce unsuccessful attempts to avoid or control pain and thus focus on engaging in valued activities and pursuing meaningful goals will be measured across all groups. The items on the CPAQ are rated on a 7-point scale from 0 (never true) to 6 (always true). To score the CPAQ, add the items for Activity engagement and Pain willingness to obtain a score for each factor. To obtain the total score, add the scores for each factor together. Higher scores indicate higher levels of acceptance
6. psychological inflexibility Psychological Inflexibility in Pain Scale (PIPS) 16-item scale used to assess psychological inflexibility (i.e. avoidance, acceptance, fusion, values orientation, dirty discomfort) in people with chronic pain will be measured across all groups. Respondents are asked to rate items on a 7-point scale that ranges from 1 (never true) to 7 (always true). Higher scores indicate greater levels of psychological inflexibility.

Other Pre-specified Outcome Measures:

1. Mindfulness based alternative approaches (MBAA) Do individuals with NF1 utilize the MBAA more readily because they are on the mobile application, via Five Facet Mindfulness Questionnaire. 39-item self-completed questionnaire measuring the five facets of mindfulness: Observing (8 items), Describing (8 items), Acting with awareness (8 items), Non-judgmental (8 items), and Non-reactive (7 items). Participants rated the items on a five-point Likert scale (1 = never or very rarely true to 5 = very often or always true), each facet score ranges from 8 to 40, except for the non-reactive facet which ranges from 7 to 35.

Study Population

A convenience sample of 108 adults with NF1 aged 18-34 will be recruited through mail merge and emails, Internet advocacy web forums (NF Network, NF Northeast:

Number of Participants

A convenience sample of 108 adults with NF1 aged 18-34 will be recruited through mail merge and emails, Internet advocacy web forums (NF Network, NF Northeast: see letters of support).

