5.1.1 Study Date Range and Duration

We predict the pilot RCT to take 18 months to complete (February 1, 2021 to August 2022). The patient networks that we are recruiting from have over 25000 adults across both groups. A conservative estimate of 20% of individuals should be within the appropriate age criterions (~5000). Given that we are seeking to fulfill 36 in each group for a total of 108 for the Pilot RCT and taken in account of a conservative 20% refusal rate. We should not encounter an issue with total number of individuals enrolled within the study within the time frame.

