5.3 Study Population

A convenience sample of 108 adults with NF1 above the age of 18 will be recruited through mail merge and emails, Internet advocacy web forums (NF Northwest and NF Network).

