5.3.1 Number of Participants

A convenience sample of 108 adults with NF1 aged 18-34 will be recruited through mail merge and emails, Internet advocacy web forums (NF Network, NF Northeast: see letters of support).

Power Analysis: An a priori power analysis conducted through G*Power (Universität Kiel, v. 3.1.9.2) estimated a conservative sample size analysis for the RCT. We are expecting a total of 140 participants, given the length of the trial, we estimate 20% attrition rate of the final sample, giving us a total sample of (n=36) per group, for a final sample size of 108. The power analysis is based on previously utilized research in which estimated effect sizes ranged from 20 to 40 individuals per group (52). We will attempt to enroll equal numbers of male and female individuals to evaluate gender differences through urn randomization process.

52. Hancock, G. R. and R. O. Mueller, Eds. (2010). *The Reviewer's Guide to Quantitative Methods. Power Analysis*. New York, NY, Routledge.

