6.3.6 End of Study and Follow Up

At the end of the study, all participants in each group (TAU, iCanCope, iCanCope+CM) will be required to complete the identical set of assessments at intake, minus demographic information. Individuals who prematurely left early or who withdrawn from the study will not be asked to complete the end of the study survey. Additionally, individuals with access to the iCanCope mobile application license will end and will not be able utilize the mobile application until the follow-up is complete. For individuals who did not have access to the iCanCope mobile application they will continue not having access to the mobile application.

All participants in each group will complete a 6-week post discharge follow-up. The follow-up will be identical to the discharge evaluation. Individuals will be emailed a secured email by the research assistant to complete the survey one day before the 6-week survey. All participants will have a one-week (7days) to complete the assessment, and a reminder email will be sent on the last day of the survey to the participants. Individuals will not be required to complete but will be encouraged to do so.

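### The plan uses 108 both as the number recruited and as the number left after 20% attrition, and never says how many will be randomised

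*Combined protocol and SAP*

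**What the plan says.** Two accounts of 108 stand in the current text.

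**108 as the intake.**
- Synopsis (Study Population and Number of Participants): "A convenience sample of 108 adults with NF1 aged 18-34 will be recruited through mail merge and emails".
- Section 5.3: "A convenience sample of 108 adults with NF1 above the age of 18 will be recruited".
- Section 5.3.1, first sentence: "A convenience sample of 108 adults with NF1 aged 18-34 will be recruited".

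**108 as what remains.** Section 6.4.2, repeated in the synopsis and in 5.3.1, says "We are expecting a total of 140 participants, given the length of the trial, we estimate 20% attrition rate of the final sample", then "giving us a total sample of (n=36) per group, for a final sample size of 108". Section 5.3.1 therefore holds both accounts.

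**Text that fits either account.** Section 5.1 describes a trial in 108 adults. Section 5.1.1 sets accrual at 36 per group (108 in total) and mentions refusal, "taken in account of a conservative 20% refusal rate", but not attrition.

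**Related text.**
- Section 6.3.6 on people who leave: "Individuals who prematurely left early or who withdrawn from the study will not be asked to complete the end of the study survey".
- Section 6.4.5 codes missing data as zero.
- The stated basis for power in 6.4.2 is that "estimated effect sizes ranged from 20 to 40 individuals per group".

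**The concern.** A number cannot be both the intake and what is left after a 20% loss from that intake. The figure 140 appears only in the repeated power paragraph, and nowhere is it called the number to enrol or randomise. A team working from 5.3 and the opening of 5.3.1 would stop at 108.

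Under 6.3.6, people who leave early are not asked for the end-of-study survey, so attrition directly removes post-treatment questionnaires. Section 5.2.1 lists three primary outcomes. Two of them, pain severity and pain interference, come from questionnaires. Minutes logged on the app can still exist for someone who later leaves.

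The feasibility question is touched as well. Section 6.2.1 defines feasibility partly by accrual and dropout. Accrual is hard to judge when the target may be 108 or 140, and dropout is hard to judge against a 20% whose base is unclear.

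The power text does not settle which number was meant, because it gives group sizes where an effect size belongs. It states no effect size, standard deviation, power or test.

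**Working it through.** **Inputs from the documents.** 108 recruited (synopsis, 5.3, 5.3.1); 140 expected, 20% attrition, and a final 108 or 36 per group (6.4.2); three arms (6.1.1), with equal allocation implied by 36 per group.

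**1. The plan's own step from 140 to 108.**
- 20% of those starting: 140 × 0.8 = 112, or 37.3 per arm, against the stated 108 and 36.
- Rounding down within arms recovers the stated figure: 140/3 = 46.7, down to 46; 46 × 0.8 = 36.8, down to 36; 36 × 3 = 108.
- Without rounding, the loss from 140 to 108 is 32/140 = 22.9% of those starting, or 32/108 = 29.6% of the final sample.

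The step is approximate, and rounding can explain it.

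**2. What remains under each reading.** The text attaches the 20% to the final sample, so two bases are shown:
- share of those enrolled: remaining = N × 0.8
- share of the final sample: remaining = N / 1.2

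| Enrolled | 20% of enrolled | 20% of final sample | 36 per arm met? |
|---|---|---|---|
| 140 | 112 (37.3 per arm) | 116.7 (38.9 per arm) | yes |
| 108 | 86.4 (28.8 per arm) | 90 (30 per arm) | no |

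With 108 enrolled, the shortfall against the stated final sample is 108 − 86.4 = 21.6 people (7.2 per arm), or 108 − 90 = 18 people (6 per arm).

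**3. What those sizes can detect (illustration).** The documents state neither sidedness nor power. Assumed here: two-sided 0.05, 80% power, no multiplicity correction, observed cases only, noncentral t. Section 5.2.1 defines the primary pain outcomes as within-group change, so the paired test comes first. The between-arm comparison of pain is a secondary question (6.2.1, 6.4.3.2).

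- Within group: df = n − 1, noncentrality = d√n, with d the mean change divided by the SD of change.
- Between arms: df = 2n − 2, noncentrality = d√(n/2), with d the difference in means divided by the SD.

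| Per arm | Within-group change | Between-arm difference |
|---|---|---|
| 29 | 0.54 | 0.75 |
| 36 | 0.48 | 0.67 |
| 37 | 0.47 | 0.66 |

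The between-arm effect detected with 80% power at 36 per arm (0.67) has about 71% power at 29.

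**The case against.** The best defence is that 6.4.2 does describe a flow: 140 expected, 20% lost, 108 left. In the synopsis and in 5.3.1 this follows closely on the sentence about recruiting 108, so that sentence may be shorthand for the final sample. On that reading there is no shortfall. The reading is available, but no section confirms it, and 5.3 gives 108 recruited without mentioning 140. The ambiguity stands; a loss to 86 is not established.

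A second defence is that 6.4.5 codes missing data as zero, so the number analysed may not fall at all. That is correct for the number analysed. The number with observed questionnaire data still falls, and whether coding as zero is sound is a separate matter.

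Third, this is a pilot and feasibility is its main question. That limits the consequences but does not remove the contradiction.

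Stronger readings are tempting, and the documents do not support them:
- *The trial will fall short of its sample size.* This follows only if enrolment stops at 108.
- *The attrition arithmetic is wrong.* Rounding down within arms gives 108.
- *135 must be enrolled.* It is true that 108/0.8 = 135, but no section names 135 as a target.
- *The 20% refusal rate removes a further fifth of the sample.* Section 5.1.1 uses refusal only to argue that the recruitment pool is large enough, and does not link it to 108 or 140.
- *The trial is underpowered.* No target effect is stated, so this cannot be judged.

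**Conclusion.** The inconsistency is certain; the shortfall is conditional. With 140 randomised, the stated 36 per group is met. With 108 recruited, between 86 and 90 people (29 to 30 per arm) would have observed post-treatment questionnaires, against a stated 108 (36 per arm).

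This rests on equal allocation, on attrition of exactly 20% spread evenly over the arms, and on people who leave early providing no end-of-study questionnaire, as 6.3.6 implies. The detectable effects are illustrative, since alpha sidedness, power and test are assumed. Going from 36 to 29 per arm raises the detectable within-group change from about 0.48 to 0.54 standard deviations. The practical impact is modest in a pilot, but the text should be corrected because both accrual and dropout are to be reported as feasibility results.

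**What to change.** In the synopsis and in 5.1, 5.1.1, 5.3, 5.3.1 and 6.4.2, state the same three things: the number randomised; one attrition rate, defined as a share of those randomised and tied to a time point (discharge or the 6-week follow-up); and the resulting number with observed questionnaire data. Use whichever of these matches the true enrolment target:

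- *108 will be randomised (36 per arm). We expect 20% of those randomised to have no questionnaire data at [time point], leaving about 86 (29 per arm).*
- *140 will be randomised. We expect 20% of those randomised to have no questionnaire data at [time point], leaving about 112 (37 per arm).*

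In 6.4.2 and its repeats, replace the sentence giving group sizes as effect sizes with a precision or detectable-effect statement for the chosen size. It should match the planned comparison (within-group change for the primary pain outcomes), label its assumptions, and say that it was computed for a fixed size. The values in the working can be used. If the G*Power inputs survive, report them.

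**Cost.** Text only. No participants are added, because the option chosen must match the existing target. If that target is 108, the option of 140 would add 140 − 108 = 32 people and should not be used. The downside is candour: with 108 as the enrolment number, the stated final sample falls from 108 to about 86, and the detectable effects rise as shown.

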6.4.3 Planned Analyses

Statistical procedures and models have been selected according to the research questions being investigated and the types of data available. We will use $\alpha < .05$ but will use appropriate corrections for multiple tests. Statistical analyses will be conducted by principal investigator using SPSS, SAS, or R with consultation from the coinvestigators. Using logistic regression for categorical and ANOVA for continuous measures, we will conduct preliminary analyses of the adequacy of the randomization procedure, the comparability of baseline measures across conditions, and the possible need for covariates in the analyses of treatment outcome data.

For the primary first outcomes: Can we identify the feasibility of the *iCanCope-NF* program? This will be evaluated using general linear model of count data (logins, dropout rates, completion of outcome measures, engagement activity, (i.e. user and aggregate levels). Additionally, the proportional changes will be evaluated using an ANOVA. Due to potential missing data assumptions, a Cox regression will evaluate for differences in relationship between pre-and post. For second primary outcome: what are perceptions regarding intervention acceptability and satisfaction; and what are the levels of engagement with the intervention? Aggregate values will be summed and standardized through a (z-score analysis) to ensure equal representation of groups. Lastly, for the levels of engagement and number of activities tried/TSN exercises will be examined with linear and non-linear Mixed-effects Models (LMM) with autoregressive 1 correlation structure (AR1) to test between conditions, while allowing for intra-participant serial correlation and unequal variance and covariance structure across time.

Secondary analyses will explore three research questions: (1) Does smartphone program (*iCanCope-NF*) compared with control condition lead to differences in pain and pain-related activity limitations, sleep functioning, emotional functioning (depression, anxiety), pain catastrophizing, self-efficacy, knowledge, psychological flexibility immediately post-treatment (T2)? This will be evaluated by incorporating an estimating equation approach to understand the differences in scores and using a sequential multilevel logistic regression models to estimate the independent and combined effects of proposed time-varying (contextual) variables on the probability of pain levels. We will also test interaction effects between stable/trait-level participant characteristics and contextual variables. (2) Does the *iCanCope-*

NF + CM increase the usage of the *iCanCope-NF* program as compared to *iCanCope-NF* without CM, and do their corresponding levels of pain and pain-related activity decrease? This will be evaluated between the two intervention groups and using the difference in nominal data sets, and simple qualitative analyses. (3) Do individuals with NF1 utilize the MBAA more readily because they are on the mobile application? To assess the moderation effect, we will include an interaction term for each separate moderator variable and key predictor of interest (two-way interaction between moderator and group for cross-sectional analysis and three-way interaction between moderator, group and time for longitudinal analysis) in the regression models and test its significance using Wald t-test.

6.4.3.1 Primary Analyses

For the primary first outcomes: Can we identify the feasibility of the *iCanCope-NF* program? This will be evaluated using general linear model of count data (logins, dropout rates, completion of outcome measures, engagement activity, (i.e. user and aggregate levels). Additionally, the proportional changes will be evaluated using an ANOVA. Due to potential missing data assumptions, a Cox regression will evaluate for differences in relationship between pre-and post. For second primary outcome: what are perceptions regarding intervention acceptability and satisfaction; and what are the levels of engagement with the intervention? Aggregate values will be summed and standardized through a (z-score analysis) to ensure equal representation of groups. Lastly, for the levels of engagement and number of activities tried/TSN exercises will be examined with linear and non-linear Mixed-effects Models (LMM) with autoregressive 1 correlation structure (AR1) to test between conditions, while allowing for intra-participant serial correlation and unequal variance and covariance structure across time.

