5.2 Outcome Variables

5.2.1 Primary Outcome Variables

Primary Outcome Measure:

1. Engagement Activity

Total minutes logged on the mobile application will be evaluated between the two groups using the mobile application.

[Time Frame: through the completion of the study, on average 4 months.]

2. Pain Severity

A comparison within groups change of pain severity measured by the Brief Pain Inventory-Short Form. Respondents rate items on a 0-10 scale to indicate the pain severity and interference, and the total score is the mean of each subfactor. The higher the score indicates more severity and interference of pain.

[Time Frame: through the completion of the study, on average 4 months.]

3. Pain Interference Index

A comparison within groups change of pain interference measured by the Pain Interference Index Scale. Respondents rate items on a 0-6 scale to indicate how much pain has interfered with various activities, and the total score is the mean of the six items. Where 6 indicates high interference.

[Time Frame: through the completion of the study, on average 4 months.]

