6.4 Statistical Method

6.4.1 Statistical Design

Statistical procedures and models have been selected according to the research questions being investigated and the types of data available. We will use $\alpha < .05$ but will use appropriate corrections for multiple tests. Statistical analyses will be conducted by principal investigator using SPSS, SAS, or R with consultation from the coinvestigators. Using logistic regression for categorical and ANOVA for continuous measures, we will conduct preliminary analyses of the adequacy of the randomization procedure, the comparability of baseline measures across conditions, and the possible need for covariates in the analyses of treatment outcome data.

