6.4.3.2 Secondary Objectives Analyses, if applicable

Secondary analyses will explore three research questions: (1) Does smartphone program (*iCanCope-NF*) compared with control condition lead to differences in pain and pain-related activity limitations, sleep functioning, emotional functioning (depression, anxiety), pain catastrophizing, self-efficacy, knowledge, psychological flexibility immediately post-treatment (T2)? This will be evaluated by incorporating an estimating equation approach to understand the differences in scores and using a sequential multilevel logistic regression models to estimate the independent and combined effects of proposed time-varying (contextual) variables on the probability of pain levels. We will also test interaction effects between stable/trait-level participant characteristics and contextual variables. (2) Does the *iCanCope-NF + CM* increase the usage of the *iCanCope-NF* program as compared to *iCanCope-NF* without CM, and do their corresponding levels of pain and pain-related activity decrease? This will be evaluated between the two intervention groups and using the difference in nominal data sets, and simple qualitative analyses. (3) Do individuals with NF1 utilize the MBAA more readily because they are on the mobile application? To assess the moderation effect, we will include an interaction term for each separate moderator variable and key predictor of interest (two-way interaction between moderator and group for cross-sectional analysis and three-way interaction between moderator, group and time for longitudinal analysis) in the regression models and test its significance using Wald t-test.

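### Logins, app minutes and yes/no dropout share one linear model with no family or link, and the engagement primary outcome has no single designated analysis

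*Combined protocol and SAP*

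**What the plan says.** Section 6.4.3.1 (repeated from Section 6.4.3) gives the first feasibility analysis: "This will be evaluated using general linear model of count data (logins, dropout rates, completion of outcome measures, engagement activity". No error distribution, link function, transformation or handling of overdispersion follows.

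Section 5.2.1 makes app use the first primary outcome: "Total minutes logged on the mobile application will be evaluated between the two groups using the mobile application". Section 6.2.1, however, lists the comparison of engagement with and without contingency management (CM) among the secondary questions.

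Further methods are named for engagement:

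- Section 6.4.3.1 also assigns levels of engagement to "linear and non-linear Mixed-effects Models (LMM) with autoregressive 1 correlation structure (AR1) to test between conditions".
- Section 6.4.3.2, on whether CM increases use, says: "This will be evaluated between the two intervention groups and using the difference in nominal data sets, and simple qualitative analyses".

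Logistic regression appears in Section 6.4.1 for baseline work ("Using logistic regression for categorical and ANOVA for continuous measures, we will conduct preliminary analyses of the adequacy of the randomization procedure") and in Section 6.4.3.2 for pain levels. It is never assigned to dropout or completion.

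Section 6.1.2 makes gender the only factor in the urn randomization. Section 6.4.4, on covariates, is marked not applicable. Section 6.4.1 leaves covariates to preliminary testing, and Section 6.4.3.3 mentions gender only in an exploratory look at module use.

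**The concern.** Three data types sit under one model name. A normal-error linear model is a poor description of login counts, and of minutes if a few people use the app heavily. It is an unusual choice for a yes/no outcome, where its estimate is a difference in proportions with the wrong variance form.

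The larger risk is choice after the fact. Total minutes between the two app arms could be analysed by the linear model, by a mixed model, or by a nominal comparison. These answer different questions, and nothing says which one counts. Section 6.4.1 has the principal investigator run the analysis, so a choice made after seeing the data could not be told apart from a planned one.

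Leaving the randomization factor out of the between-arm models also forgoes whatever precision gender offers.

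**Working it through.** **Inputs from the documents.** The sample is given as "giving us a total sample of (n=36) per group, for a final sample size of 108" (Section 6.4.2). Alpha is 0.05; two-sided is assumed, since sidedness is not stated. The plan "will use appropriate corrections for multiple tests" but names none, so the figures below use 0.05 uncorrected. The documents give no mean, SD, skew or share of non-users for app use, so every usage distribution here is an assumption.

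**The plan's own figure.** Section 6.4.2 says: "We are expecting a total of 140 participants, given the length of the trial, we estimate 20% attrition rate". The arithmetic gives 140 × 0.8 = 112, not 108; 108/0.8 = 135; and 108 × 1.2 = 129.6, or 130. The power calculation cannot be reproduced, because no effect size, SD or target power is stated. For reference, 36 v 36 has 80% power for a standardised difference of 0.67. Below, 36 per arm is simply taken as given.

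**Method.** Power is the share of simulated trials with p < 0.05. The raw linear model for two arms is the pooled t-test on untransformed values. For lognormal minutes with coefficient of variation CV, the log-variance is ln(1 + CV²). There were 20,000 runs for minutes and 1,500 for logins. Dropout power was summed exactly over binomial outcomes.

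**Lognormal minutes, no zeros: raw v log scale**

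| CV | CM ratio 1.5 | loss | CM ratio 2 | loss |
|---|---|---|---|---|
| 0.5 | 92.4% v 95.0% | 2.6 | 100% v 100% | 0 |
| 1 | 41.7% v 53.4% | 11.7 | 84.2% v 93.8% | 9.6 |
| 2 | 15.4% v 26.7% | 11.3 | 37.2% v 62.8% | 25.6 |

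**Negative binomial logins (mean 20): raw v negative binomial likelihood-ratio test**

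| Size k | CM ratio 1.5 | loss | CM ratio 2 | loss |
|---|---|---|---|---|
| 2 | 62.7% v 65.2% | 2.5 | 96.9% v 97.8% | 0.9 |
| 1 | 36.3% v 39.4% | 3.1 | 77.4% v 81.6% | 4.2 |
| 0.5 | 20.0% v 22.1% | 2.1 | 48.5% v 53.6% | 5.1 |

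**Gamma minutes, shape 1: raw v log scale v rank test.** At ratio 1.5: 37.4%, 27.0%, 30.8%. At ratio 2: 80.4%, 62.6%, 69.9%. Here raw minutes do best.

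**Dropout 20% v 40%, 36 per arm: linear, chi-square, logistic.** 46.0%, 47.1%, 48.3%. At 45 or 47 per arm, nearer the number enrolled, the linear and logistic figures differ by 1 point or less.

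**Type I error of the linear model.** 3.5% to 5.2% for usage and 4.9% to 5.9% for dropout.

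**Zeros.** Section 6.3.1 requires no time in the app, and Section 6.4.5 codes missing data as zero. Take lognormal minutes, median 150, ratio 1.75, and log-SD 0.8, 1.0 and 1.2. Without zeros, raw v log power is 72% v 84%, 47% v 65% and 30% v 50%. With 10% zeros in both arms, raw v log(1+minutes) is 60% v 24%, 40% v 21% and 26% v 20%. The advantage of logs reverses.

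**Log-link model for mean minutes.** It gains about 1 to 11 points over raw minutes, but its model-based test runs at about 5% to 8%, so part of that gain is inflation. A permutation p-value removes the inflation, and with it most of the gain. Let total minutes T be fixed and B be the CM arm's total, with 36 per arm. The mean difference is (2B − T)/36 and the ratio is B/(T − B). The absolute log ratio and the absolute difference both rise with |2B − T|. An unadjusted permutation test of the plain ratio therefore gives the same p-value as one of the difference in means.

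**The case against.** The strongest reply is that the wording may be a slip for a generalized linear model, since it is attached to count data. That is possible, and the text does not settle it. The plan would still lack a family and link for each outcome, and one count family would not suit yes/no dropout.

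Second, mean minutes is a legitimate target for a feasibility pilot, and a log-scale analysis changes what is estimated. This stands. It is why the fix keeps the mean as the target and shows raw means.

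Third, a reader might infer that the linear model necessarily costs power on the engagement outcome, or that its tests are invalid. The documents support neither. They give no usage distribution. The large losses appear only for heavy-tailed lognormal minutes without zeros, and gamma minutes or a modest share of non-users reverse the comparison with logs. Error rates stay near 5%.

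Fourth, since several engagement methods are named, no particular loss can be pinned on the linear model. This also stands, and it moves the weight of the point to the missing designation of a primary analysis.

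**Conclusion.** The specification defect holds. One model name covers counts, minutes and yes/no outcomes without family or link. Primary outcome 1 has competing analyses and none designated. The randomization factor is fixed in no between-arm model.

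The cost in power is conditional. At 36 per arm, two-sided 0.05 and the distributions assumed above, it is about 0 to 26 points for lognormal minutes without zeros, 1 to 5 for negative binomial logins and 0 to 2 for dropout. For gamma minutes there is no loss against a log-scale or rank test. The case for change rests on a fixed, interpretable analysis suited to each data type, not on false positives or a demonstrated loss of power. For minutes, the recommended permutation test should not be expected to add power over raw means.

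**What to change.** Rewrite Sections 6.4.3 and 6.4.3.1 with one named model per outcome, with gender in each:

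- **Logins:** negative binomial regression with a log link.
- **Dropout and survey completion:** logistic regression.
- **Total minutes, the two app arms:** one designated primary analysis, a log-link model for mean minutes. Report the CM/no-CM ratio with 95% CI and show raw means beside it. Take the p-value by permutation within gender. Put the interval on the same footing, for example by inverting the permutation test: a test running at 5% to 8% implies model-based coverage of only about 92% to 95%.

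Do not use log(1+minutes). Define genuine zero use from the app log and keep it apart from missing data, amending Section 6.4.5 to match. Label the mixed-model and nominal analyses of engagement as secondary or remove them, and reconcile Section 6.2.1 with Section 5.2.1 on whether the CM comparison of engagement is primary. Replace the not-applicable entry in Section 6.4.4 with gender.

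The cost is plan wording and slightly more analysis work, best done before any data are compared by arm. Effects will be reported as ratios and odds ratios, which some readers find less direct than differences. Sample size and data collection do not change.
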